**Procedures for Evaluating Proximal Implementation Outcomes:**

**Reach Outcome:** For this study outcome, Reach (i.e. the number of individuals who are willing to participate in an initiative) is defined as the absolute number of Black cis-gender women who receive a PrEP prescription. We will also evaluate the proportion of women prescribed PrEP who had a PrEP indication. PrEP indication will not be defined using the Center for Disease Control and Prevention (CDC) PrEP indication clinical guidelines due to evidence suggesting these criteria are too restrictive and may not predict risk. Instead we will define PrEP eligibility based on the CDC’s guidance summary criteria, deeming those PrEP eligible who meet any of the following criteria for cis-gender women not living with HIV (over a 6-month timeframe): HIV-positive sex partner, bacterial STI (gonorrhea or syphilis), more than one sex partner, inconsistent condom use, sex for exchange of goods, or being in a high-prevalence network. This data will be obtained based on the sexual risk screener (a component of implementation strategy) documented in the chart during patient visits.

**Procedures.** Data will be collected from the university’s electronic medical record, looking at visit data for all cis-gender women with clinic visits during the pilot timeframe. We will be able to extract prescription data directly, but PrEP eligibility and referral will require review of chart documentation.

**Preliminary Effectiveness Outcome:** To evaluate effectiveness of PrEP4Her, we will determine increases in PrEP prescriptions over-time. We will also evaluate what patient factors are associated with PrEP prescription.

**Procedures.** A data extraction of the UAB electronic medical record will be done (as described above) at 3-month time intervals after implementation of PrEP4Her (i.e. baseline, 3-months and 6-months’ time). We will collect the following patient demographics: age, race, ethnicity, and insurance status.

**Statistical analysis.** Frequencies for prescription will be reported overall and for each independent variable (i.e. patient demographics), at each of the 3 time points (baseline, 3 months and 6 months). Means, standard deviations and t-test comparisons between those referred and prescribed PrEP will be reported for continuous

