### Objectives

(Primary manuscript) Mixed methods paper evaluates the implementation outcomes, using the RE-AIM framework, of the PrEP4Her intervention in a low barrier gynecology setting.

(Primary/Fidelity) Described fidelity to PrEP4Her from the end-user perspective. Describe results from survey, compare/contrast with EHR review (EHR data confirms the number of PrEP prescriptions)

**Study population:** Reproductive aged women 18-45 who received the PrEP4Her intervention as a component of their standard care from January 2023 – August 2024 [Pre-implementation stage Jan – July 2023; PrEP4Her implementation July 2023 January 2024; Pilot January 2024-August 2024].

**PreP4HER components** - Universal sexual history screener, synchronous PrEP training, job aides [pocket cards with CDC PrEP guidance and 5Ps, EHR documentation/order aids, educational materials, asynchronous training on communication strategies

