#### Quantitative data

1. Visits per period (of intervention) with number of PrEP prescriptions
  - a. Patient visits by intervention period; total n=4161
  - b. PrEP prescriptions per period; n=11
2. EHR review (to confirm PrEP prescriptions)
  - a. Total charts reviewed n= 4635; missing =6
3. Demographics of all patients
  - a. Race
  - b. Sex at birth assignment
  - c. Gender in EHR
  - d. Lab results
    - i. Chlamydia
    - ii. Gonorrhea

- iii. Syphilis
- iv. HIV

4. Demographics of patients with a PrEP prescription

- a. Race
- b. Sex assigned at birth
- c. Gender assigned in HER
- d. Lab results
  - i. Chlamydia
  - ii. Gonorrhea
  - iii. Syphilis
  - iv. HIV

5. Sexual health pre-screener survey; n=1135

- a. Sociodemographics
  - i. Race
  - ii. Sex assigned at birth
  - iii. Gender in EHR
  - iv. Lab results
    - 1. Chlamydia
    - 2. Gonorrhea
    - 3. Syphilis
    - 4. HIV
- b. Sexual health pre-screener outcomes; n=1135
  - i. Types of sexual behaviors
  - ii. Gender of partners
  - iii. Sexually active in last year
  - iv. Number of sexual partners in past year
- c. Data on when participants were seen (by month/year)

6. Post visit (fidelity) survey data; n=242

- a. Demographics
  - i. Race
  - ii. Education
  - iii. Employment
  - iv. Insurance
  - v. Estimated household income
  - vi. Reason for visit
  - vii. Anal sex in past 6 months
  - viii. Condom use history
  - ix. Number of partners
  - x. Gonorrhea or syphilis diagnosis, past 6 months
  - xi. Partner living with HIV and not on medication
  - xii. Did provider take sexual history?

- xiii. Saw educational materials during visit?
- xiv. Spoke with provider about PrEP?
- xv. Prescribed PrEP during visit?

- b. Fidelity items
  - i. Comfort discussing PrEP w/ provider
  - ii. Understood side effects of PrEP after discussion w/ provider
  - iii. Provider discussed how to pay for PrEP
  - iv. Felt confident could take PrEP daily after visit
- c. Row percentages -Talked to doctor about PrEP and demographics

7. PrEP prescriptions data with physician and intervention period

- a. Demographics of patient prescribed; n=11
  - i. Race
  - ii. Age
  - iii. Lab results
  - iv. Earliest Emtricitabine-Tenofovir
  - v. Study Prescription Date
  - vi. Order Date

8. Number of women with a PrEP indication seen during the study visit (no indication/STI in last 12 months/multiple partners/STI in last 12 months and multiple partners); n=4241

- a. Data by visit date

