## **Paper 1: Mixed Methods Paper, guided by REAIM**

Procedures for Evaluating Proximal Implementation Outcomes:

**1. Reach:** For this study outcome, Reach (i.e. the number of individuals who are participated in PrEP4Her) is defined as the absolute number of Black cis-gender women who receive a PrEP prescription. We will also evaluate the proportion of women prescribed PrEP who had a PrEP indication.

PrEP eligibility is based on the CDC's guidance summary criteria, deeming those PrEP eligible who meet any of the following criteria for cis-gender women not living with HIV (over a 6-month timeframe): HIV-positive sex partner, bacterial STI (gonorrhea or syphilis), more than one sex partner, inconsistent condom use, sex for exchange of goods, or being in a high-prevalence network. This data will be obtained based on the sexual risk screener.

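### SAP item 8 has no 'not assessed' row: 4241 are classified by PrEP indication, but the named source of partner data covers 1135

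*Combined protocol and SAP*

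**What the plan says.** In the SAP, Outcomes Assessment, Quantitative data, item 8 counts women with a PrEP indication in four classes: "no indication/STI in last 12 months/multiple partners/STI in last 12 months and multiple partners); n=4241". Item 8a adds a breakdown by visit date. There is no class for unknown, missing or not assessed.

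The inputs are described elsewhere:

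- **Partner number.** Item 5 is "Sexual health pre-screener survey; n=1135", and one of its listed outcomes is "Number of sexual partners in past year". For eligibility, Paper 1 (Reach) says "This data will be obtained based on the sexual risk screener".
- **Protocol counterpart.** Aim 3, Reach Outcome, says "This data will be obtained based on the sexual risk screener (a component of implementation strategy) documented in the chart during patient visits". Its procedures add that "PrEP eligibility and referral will require review of chart documentation".
- **A second place where partner number is asked.** Item 6 is "Post visit (fidelity) survey data; n=242".
- **STI results.** Item 3 lists laboratory results under the demographics of all patients, without the number tested.
- **Calendar.** The SAP's study population spans "Pre-implementation stage Jan – July 2023; PrEP4Her implementation July 2023 January 2024; Pilot January 2024-August 2024". The screener is listed there as a PrEP4Her component.

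**The concern.** Two of the four classes need a partner count, and the class without an indication needs one too, to rule multiple partners out. The named source of that count has far fewer records than the base being classified. With no row for the unassessed, the table cannot separate a woman who was asked and did not report multiple partners from one who was never asked. The same applies on a smaller scale to STI: a woman with no test looks like a woman with a negative test.

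Item 8 is the SAP's only count of women with an indication, so readers will naturally set the 11 prescriptions against it. If unassessed women are counted as having no indication, need on the partner criterion looks smaller than it is. Because the screener is part of the intervention, the amount of missing data may also change with calendar time. Item 8a could then show measured need changing for reasons unrelated to true need, beside an effectiveness outcome that is itself read over time.

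This problem is separate from which criteria or look-back window define an indication. It arises under any definition that uses partner number.

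**Working it through.** The 4241 is an observed count with no formula behind it, so there is nothing to reproduce. It matches neither of the other totals in the list: 4241 − 4161 visits = 80, and (4635 − 6) charts − 4241 = 388.

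**Step 1: coverage.** Inputs are 1135 (item 5) and 4241 (item 8). Assume that both count women and that the 1135 are nested in the 4241.

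- With a screener record: 1135 / 4241 = 26.8%.
- Without: 4241 − 1135 = 3106, and 3106 / 4241 = 73.2%.
- With other bases, coverage is 1135 / 4161 = 27.3% or 1135 / 4635 = 24.5%.
- Adding all 242 post-visit surveys with no overlap: 1135 + 242 = 1377, or 32.5%. That leaves 2864 (67.5%) without a partner count.

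**Step 2: effect on the multiple-partner share.** If unscreened women are shown as not having multiple partners, displayed share = coverage × share among the screened. The documents give no share, so a range is assumed. The last column treats every unscreened woman as having multiple partners: displayed share + 73.2%.

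| Assumed share among screened | Displayed in item 8 (lower bound) | Upper bound |
|---|---|---|
| 10% | 2.7% | 75.9% |
| 20% | 5.4% | 78.6% |
| 30% | 8.0% | 81.3% |

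**Step 3: effect on any indication.** With STI prevalence s known for everyone and independent of partner number, any indication = s + (1 − s) × p. Take s = 5% and p = 20%, both assumed.

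- Full assessment: 0.05 + 0.95 × 0.20 = 24.0%.
- Item 8 layout: 0.05 + 0.95 × 0.20 × 0.268 = 10.1%.

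The displayed figure is about 42% of the full one (10.1 / 24.0), against 27% for partners alone. Unscreened women with a positive STI result remain in the STI class, although some may belong in the combined class.

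**Step 4: pattern by visit date.** Assume that the 4241 are spread evenly over the 20 months from January 2023 to August 2024, with a constant true share of 20%.

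- Screener used only in the last 14 months: coverage 1135 / (4241 × 14/20) = 38.2%. Displayed share is 0% before and 7.6% after.
- Screener used only in the last 8 months: coverage 1135 / (4241 × 8/20) = 66.9%. Displayed share is 0% before and 13.4% after.
- Equal coverage throughout: a flat 5.4%, with no rise.

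A spurious rise therefore needs coverage that grew over time, and a base that includes the earlier months.

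**The case against.** Item 8 is one line in an inventory of datasets. It does not say how missing data are coded, and item 2 of the same list does report a missing count, so the absence of a row does not prove that missing was treated as negative. The protocol expects chart review for eligibility, and its Table 4 lets a medical assistant or a provider chart the sexual history. Partner data may therefore exist beyond the 1135 records. The unit and nesting of the two counts are not stated. STI results do not depend on the screener. No stated outcome uses 4241 as its denominator: Reach is a number of Black women prescribed PrEP, its companion proportion is taken among women prescribed, and effectiveness concerns prescriptions.

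Most of this stands and limits the point. A reader might infer that every unscreened woman must be coded as having no indication; the documents do not support that, because no coding rule is written and an unscreened woman with a positive STI result has a class of her own. A reader might also infer that the table is bound to show need rising when PrEP4Her starts. That is not supported either: screener counts by month are not given, and Paper 1 limits the Reach visit data to the pilot timeframe, so the 4241 may not include the pre-implementation stage.

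The objection does not supply the missing row. The SAP names no partner source for item 8 other than the screener, and the protocol's wording on chart review can equally mean retrieving the screener from the chart. Even the post-visit survey, counted in full, leaves about two thirds without a partner count.

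**Conclusion.** The point holds for the partner component and, conditionally, for its pattern over time. It should be fixed, but no test, sample size or decision rule depends on it.

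As laid out, item 8 mixes never asked with no indication. If units match, the screened are nested, and no other charted source is used, 73% of the base lacks a partner count and the multiple-partner share shows at about 27% of its value among the screened. If the unscreened resemble the screened, that is roughly a 3.7-fold understatement (4241 / 1135). Any indication is diluted less. The artificial rise is a risk that depends on coverage by month and on the period the 4241 cover.

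It would go too far to conclude that item 8 understates PrEP indication overall as Reach defines it. Item 8 uses a 12-month STI window where Reach uses 6 months, which may overstate. It also leaves out condom use, a partner with HIV, exchange sex and network prevalence, which understates. The net direction is unsettled. The Reach proportion among the 11 women prescribed is affected only if some of them were unscreened and are classified in this way; each such woman would move it by 1/11, or 9.1 percentage points.

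**What to change.** Revise item 8 as follows:

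1. Add a row for partners not assessed and a row for STI not tested.
2. State the source and coding of partner data, including whether charted histories or the post-visit survey contribute. State whether 4241 counts women or visits, which period it covers, and how it relates to 1135, 4161 and 4635.
3. Report multiple partners among women with partner data from any stated source, and STI among women tested, with the number assessed beside each.
4. Give bounds for the unassessed. If 20% of the screened report multiple partners, these are 5.4% to 78.6%.
5. For item 8a, show screener coverage and STI testing rate by period. Item 5c already lists when screened women were seen, by month and year. Compare the partner criterion over time only among assessed women.

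The cost is SAP wording and a re-tabulation, largely of data already held. The downside is smaller denominators and a caveat that screened women may differ from unscreened women, so the assessed-only figures should not be presented as clinic-wide prevalence.

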## **Paper 1: Mixed Methods Paper, guided by REAIM**

Procedures for Evaluating Proximal Implementation Outcomes:

**1. Reach:** For this study outcome, Reach (i.e. the number of individuals who are participated in PrEP4Her) is defined as the absolute number of Black cis-gender women who receive a PrEP prescription. We will also evaluate the proportion of women prescribed PrEP who had a PrEP indication.

PrEP eligibility is based on the CDC's guidance summary criteria, deeming those PrEP eligible who meet any of the following criteria for cis-gender women not living with HIV (over a 6-month timeframe): HIV-positive sex partner, bacterial STI (gonorrhea or syphilis), more than one sex partner, inconsistent condom use, sex for exchange of goods, or being in a high-prevalence network. This data will be obtained based on the sexual risk screener.

### **Procedures:**

- a. **Visit data for all cis-gender women with clinic visits during the pilot timeframe**
- b. **PrEP prescription data**

- c. **PrEP eligibility and referral data**
- 2. **Preliminary Effectiveness:** Defined by increases in PrEP prescriptions over time. We will also evaluate what patient factors are associated with PrEP prescription.

**Procedures:**

- a. **Frequencies of PrEP prescriptions by**
- b. **Report demographics of patients prescribes PrEP**
- 3. **Adoption:** Defined as the proportion of key-stakeholders within our pilot site who were willing to initiate our implementation strategy.

**Procedures:**

- a. **Number of providers/staff who attended PrEP4Her trainings**
- b. **Track clicks for asynchronous training attendance**
- c. **RedCap survey item for providers – Did you access these training materials to aid in the PrEP implementation at the GYN Continuity Clinic?**
- d. **Chart review – number of patients seen during pilot who receiving a sexual history screener.**
- 4. **Acceptability:** Extent to which key stakeholders, both provider delivering the intervention and Black cis-gender women receiving it, felt PrEP4Her was acceptable.

**Procedures:**

- a. **IDIs and key informant interviews, grounded in Sekhon et al. [prospective/concurrent/retrospective acceptability]**
- b. **We also have AIM data – would that go here?**
- 5. **Feasibility:** Measure whether PrEP4Her is appropriate for a larger, full-scale implementation trial by surveying out key-stakeholders prior to interviews (conducted to assess acceptability).

**Procedures:**

- a. **Validated scale Feasibility of Intervention Measure (FIM)**

**Paper 2: Fidelity Outcomes**

- 1. **Fidelity:** Degree to which our implementation strategy (PrEP4Her) was implemented as designed, from end user perspective.

**Procedures: Patient fidelity survey outcomes.**
